7.2 Treatment Assignment

Participants who provide informed consent and undergo screening assessments receive a unique participant number. This assignment of participant numbers occurs at the screening and baseline visit and serves to identify data in an anonymous fashion. Participant eligibility will be established at the conclusion of the baseline evaluations (prior to randomization and first dose of IMP at Week 0). Participants who meet all entry criteria will then be randomized in a 1:1 allocation to receive either topical sirolimus 2% or placebo ointment according to a computer-generated randomization list.

The participants and the investigator staff (except the unblinded pharmacist) will be blinded to the treatment assignment. Participants who withdraw from the study following informed consent, but before randomization to study treatment, will be classified as screen failures.

7.4 Blinding

This is a double-blind study. All study staff (which includes the investigator, sub-

investigators, other site staff) and participants will be blinded to the treatment allocation throughout the trial.

The blinded study treatment assignments for individual participants will be maintained by a Central System used by the study pharmacy. Emergency unblinding will be available via the central system in a case where the identity of the IMP must be known in order to treat an emergent adverse experience for an individual patient.

If the treatment blind is broken for a participant in the treatment period, the participant in question will be withdrawn from the treatment period and moved into the follow-up period.

During the study, investigators will not receive central laboratory data that have the potential to unblind a subject's treatment assignment.

7.5 Prohibited concomitant medications

Participants may take other medications for treatment of the symptoms associated with EBS, so long as they do not fall into any of the prohibited medications category (see exclusion criteria).

8.0 Study Assessments

Table 2 shows the schedule of assessments for the study. The investigators (medically qualified) are to conduct all study assessments. The investigator or designee must obtain written informed consent prior to performing any of the study information that will be recorded in source documents.

If a visit cannot be scheduled on the appropriate date, the visit should be re-scheduled as close as possible to the planned date, ideally within 3 days.

The study participants and caregivers will be given specific instructions about gentle skin care and avoid possible irritants on the treated area during the entire study. Patients will also be instructed to inspect the plantar surface daily to ensure no trauma.

8.1 Medical history and examination

A complete medical history will be taken at the Screening Visit. Information from the medical history is important to establish the baseline condition of the participant and will impact the safety monitoring assessments during the study. Any significant medical conditions affecting the participant in the past 5 years should be recorded. The history should include the following:

- A thorough review of systems, including any past or current conditions
- Prior surgical procedures
- Full medication history
- Prior immunosuppressive therapies, including type, number, and duration
- Allergies and significant allergic reactions
- Significant infections, or history of recurrent infection, including urinary and respiratory tract infections
- Smoking history (current or previous smoker, number of packs per day smoked)
- Full physical examination will be performed by an experienced medical practitioner.

8.2 Epidermolysis bullosa simplex history

Details of the participant's EBS history will be collected (e.g. dates of symptom onset, diagnosis) and recorded. These data are critical for establishing subject eligibility, as well as establishing a baseline for subsequent clinical assessments.

8.3 Primary outcome measures

1. Foot function utilizing the validated Foot Health Status Questionnaire (FHSQ) as a change from baseline to the end of each treatment.
2. Safety and tolerability of topical sirolimus 2% ointment (serum trough sirolimus levels, monitoring for adverse events).

8.4 Secondary Outcome Measures

1. Plantar defect size measurements using 3D photography (% change in total defect area) from baseline to the end of each treatment.
2. EB Disease Activity and Scarring Index (EBDASI) feet activity scores as a change from baseline to the end of each treatment
3. Quality of life assessment in EB (QOLEB) as a change from baseline to the end of each treatment.
4. Itch severity measured using 5-D Pruritus Scale as a change from baseline to the end of each treatment.
5. Participants will wear a FitBit® for the duration of the study to assess number of steps walked per day as a change from baseline to the end of each treatment.
6. Changes in foot plantar pressure measurements before and after treatment using the Podotech Elftman Foot Scanner from baseline to the end of each treatment.
7. Molecular biology study of skin biopsies assayed for mTOR pathway inhibition (e.g. determination of phosphoprotein inhibition included ribosomal protein S6, S6 kinase and/or eIF-4E binding protein) as a change from baseline to the end of each treatment.

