4.0 Objectives and Scientific aims

Aim 1: To assess the safety of topical sirolimus 2% use in the treatment of plantar lesions in epidermolysis bullosa simplex (EBS).

Aim 2: To assess the efficacy of topical sirolimus 2% to improve the clinical severity of lesional skin, including pain and itch symptoms.

Aim 3: To assess improvement in walking ability.

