5.2 Inclusion criteria

- Diagnosis of EBS
- Minimum EBDASI feet activity score of 2/10
- Healthy male or non-pregnant female
- Age ≥4 years old or older

- Ability to complete 7 study visits, each for approximately 30-60 minutes, including 3 scheduled phone calls within a 40-week period
- Anticipated life expectancy ≥ 52 weeks
- Males and females of childbearing potential should be using an effective means of contraception.
- Laboratory values within the range of normal unless the PI feels they are not clinically relevant.

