6.0 Study Design and Intervention

6.1 Study Design

This study is a prospective, double-blind, randomized, placebo-controlled crossover study at Stanford University School of Medicine, USA. It includes a 6-week screening period, followed by a 4 Phase Pilot Clinical Trial (see Table 2).

Screening: Up to 6 weeks

Phase 1: 12-week treatment period

Phase 2: 4-week wash-out period

Phase 3: 12-week treatment period

Phase 4: 4-week wash out period

Follow-up: 8 weeks after end-of-trial visit.

This research study is expected to take approximately 40 weeks. There will be 2 different parts of the study which the subject may receive for initial treatment period either (a) placebo (no drug) or (b) study drug for 12 weeks, during their enrollment in the 40-week study. After the initial 12-week period, there will be a washout period consisting of 4 weeks, before starting secondary treatment. During the secondary treatment period, a switch will occur and subject will receive either the (a) placebo (no drug) or (b) study drug depending on which treatment was received initially. At some time point during the 40-week study, at least both feet will receive study drug. There will also be a post-treatment visit at week 16 and week 32, with a post study phone call at Week 40. The end of treatment period will occur at Week 12 and Week 28, with the final in-person study visit occurring at week 32. Structured phone calls made by a physician will occur at Week 2, Week 14, Week 18, and Week 40.

The EBDASI feet score needs to be within 20% of baseline to progress to Phase 3. If subject's score does not meet this criteria the Phase 2 wash-out can be extended to 6 weeks.

Treatments are switched after Phase 2.

In-person study visits:

- Week 0 (screening/baseline)
- Week 4
- Week 12
- Week 16
- Week 20
- Week 28
- Week 32

Structured physician phone-call will be scheduled at:

- Week 2
- Week 14
- Week 18
- Week 40

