6.4 Screening/Baseline Period

Before any study-specific interventions are performed, the appropriate written informed consent must be obtained for the trial and a separate consent for skin biopsy, which is an optional additional procedure.

To assess subject eligibility, all screening assessments as follows should be completed: eligibility criteria, medical history and physical exam, weight and height, demography, vital signs, concomitant medications, Epidermolysis Bullosa Diseases Activity Score (EBDASI), Quality of Life in Epidermolysis Bullosa (QOLEB), collection of blood for: metabolic panel, complete blood cell count with differential, urinalysis, lipid profile.

The participant will also be initiated in how to use the Fitbit and completion of daily diaries and the various different questionnaires to be used in the trial.

6.5 Treatment Period – Phase 1

Participants who meet all eligibility criteria will be randomized 1:1 to receive either topical sirolimus 2% or placebo ointment. The on-site Registered Nurse will teach the participant how to apply the ointment to both feet and will administer the first dose of IMP at week 0. Subsequent twice daily application of IMP to both feet will be performed by the participant, this will continue for 12 weeks.

6.6 Wash-Out Period – Phase 2

After completion of Phase 1 the participant will stop applying the IMP to the feet for a period of 4 weeks at which point their baseline activity will be assessed. If their EBDASI feet score is within 20% of baseline they can proceed to Phase 3.

6.7 Treatment Period – Phase 3

Participants who received topical sirolimus 2% during phase 1 will switch to placebo ointment and vice versa. Twice daily application of IMP will be continued by the participant for a further 12 weeks. The trial will remain double-blinded throughout.

6.8 Wash-Out Period – Phase 4

After completion of Phase 3 participants will enter a further 4-week wash-out period where they will stop applying the IMP to their feet. At the end of Phase 4 they will attend for their final end-of-trial physician visit.

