Defect area measurement using Visitrak	X		X	X		X		X	X	X	
2D photography of feet	X		X	X		X		X	X	X	
EBDASI feet score	X		X	X		X		X	X	X	
EBDASI total score	X			X		X			X		
QOLEB	X			X		X			X		
5-D Pruritus Scale	X			X		X			X	X	
Plantar pressure measurement	X			X		X			X	X	
Study drug collection/weighing/accountability	X		X	X		X		X	X		
Supervise study drug self-administration ¹	X		X			X		X			
Fitbit (daily)	X	X	X	X	X	X		X	X	X	X

Collection of blood for:											
Urine Pregnancy Test ^h	X		X	X		X		X	X	X	
				(EOT) ^a					(EOT) ^a		
Visit Number	1	□ ^b	2	3	□ ^b WASH-OUT	4	□ ^b	5	6	7	□ ^b
Study Week	Week 0	Week 2	Week 4	Week 12		Week 16	Week 18	Week 20	Week 28	Week 32	Week 40
Sirolimus trough level			X	X				X	X	X**	
Urinalysis	X			X		X			X	X	
CBC	X		X	X		X		X	X	X	
Metabolic panel	X		X	X		X		X	X	X	
Lipid profile	X		X	X		X		X	X	X	
Skin biopsy (optional)	X			X		X			X		
Structured phone-call		X				X		X			X

If a washout period is needed prior to baseline, subject has up to 6 weeks before starting treatment.

a. EOT= End of Treatment

b. After screening, subject will be randomized and enter Phase 1, the initial treatment application period. Subject will receive study drug or vehicle during this 12-week treatment period.

c. When Phase 1 is complete, a wash-out period will occur, which will last 4 weeks.

d. Phase 3 is the secondary treatment application period. The subject will receive either study drug or vehicle, switching from treatment initially used in Phase 1 during this secondary 12-week treatment period. Phase 3 may be delayed if subject has not reached 20% baseline EBDASI activity / Visitrak 2cm diameter.

e. Phase 4 will be a 4 week follow-up period after study treatment has concluded.

f. A scheduled phone call will occur at Week 40, after post treatment period at Phase 3.

g. Structured physician phone-call will be scheduled

h. Eligible female subjects of childbearing potential

i. Application occurs at the site on visit days

Table 3: Trial Objectives and Outcome Measures

Primary Objectives	Primary Outcomes

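### The step-count outcome is a change from baseline, but the plan neither defines nor guarantees any untreated step-count days before the first dose

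*Combined protocol and SAP*

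**What the plan says.** **Outcome.** Section 8.4, item 5, has participants wear a Fitbit to "assess number of steps walked per day as a change from baseline to the end of each treatment". Table 3 lists the same outcome as item e, under an objective about improvement in the majority of participants at the end of each treatment relative to baseline. No section gives a baseline window, an averaging rule or a minimum wear time.

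**Schedule.** Section 6.1 makes Week 0 the combined screening and baseline visit, the first of seven in-person visits. Table 2 has no earlier column. Consent, the first Fitbit mark and the first supervised application all stand in its Week 0 column. Section 6.5 says the nurse "will administer the first dose of IMP at week 0".

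**Time before treatment.** Section 6.1 also gives a screening period of up to 6 weeks. Section 6.4, on that period, says: "The participant will also be initiated in how to use the Fitbit and completion of daily diaries". A note to Table 2 reads: "If a washout period is needed prior to baseline, subject has up to 6 weeks before starting treatment". None of these sets a minimum interval or says that the Fitbit is worn during it.

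**Before Phase 3.** Phase 2 is a 4-week wash-out that Section 6.1 lets run to 6 weeks. The Fitbit row in Table 2 is marked in the wash-out column.

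**The concern.** Daily steps vary from day to day, so a usable baseline is an average over several untreated days. A participant handled exactly as Table 2 sets out receives the device and the first application at one visit, leaving at most part of a clinic day. Any substitute is poor. The clinic day may reflect travel, and the first treated days may already contain some treatment effect. Phase 3, in contrast, follows at least four off-treatment weeks with the device in use.

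What is at stake is a secondary outcome: each participant's change from baseline, and any crossover analysis that gives each period its own baseline. Untreated days that were not recorded cannot be recovered at the analysis stage.

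**Working it through.** The plan states no sample size, standard deviation or power for step counts, so there is no figure of its own to reproduce. The check is a count of days followed by some algebra.

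**1. Untreated days before Phase 1**
- By Table 2: device and first application at the same visit, so 0 full days.
- By Sections 6.1 and 6.4: up to 6 weeks × 7 = 42 days, with no minimum.
- Range 0 to 42; guaranteed number 0.
- The phases and follow-up in 6.1 sum to 12 + 4 + 12 + 4 + 8 = 40 weeks, which is the whole stated study length. No screening time is counted in it.

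**2. Off-treatment days before Phase 3**
- 4 weeks × 7 = 28, or 6 weeks × 7 = 42 if the wash-out is extended.

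**3. One common baseline B**
- The within-person contrast is (Y_sirolimus − B) − (Y_placebo − B) = Y_sirolimus − Y_placebo.
- B cancels, however noisy it is. The change within one period, Y − B, keeps all the error in B.

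**4. A separate baseline for each period**
- Suppose the Phase 1 baseline is taken from early treated days, when a fraction f of the effect τ is already present, and the Phase 3 baseline comes from a clean wash-out. Assume no period or carry-over effect.
- Sirolimus first: the contrast estimates (1 − f)τ.
- Placebo first: the contrast estimates τ.
- Equal-weight average of the two sequences: (1 − f/2)τ.
- For an assumed f of 0 to 0.5, the attenuation f/2 is 0 to 25%.

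**5. Noise in one participant's baseline**
- With independent days, the standard error of a k-day mean is CV/√k. The documents give no day-to-day coefficient of variation (CV); 30–40% is assumed.

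| Baseline days k | CV 30% | CV 40% |
|---|---|---|
| 1 | 30% | 40% |
| 7 | 11.3% | 15.1% |
| 14 | 8.0% | 10.7% |

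These are percentages of that person's own mean. A wider assumed CV of 60% gives 60%, 22.7% and 16.0%. They describe a single baseline, not the error of the treatment contrast.

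**The case against.** Three stronger readings are tempting, and the documents do not support them.

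**That Phase 1 has no untreated walking data at all.** Section 6.1 gives the screening period without conditions, and 6.4 places Fitbit initiation within it, apart from the first dose in 6.5. The Table 2 note names one use of the interval; it does not limit the interval to that use. Eligibility also depends on laboratory values (5.2) and must be settled before randomisation (7.2), which suggests a gap before dosing for some participants. Pre-dose days are therefore possible. What stands is that they are neither required nor defined, and that Table 2 and Sections 6.1/6.4 point different ways.

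**That the crossover comparison of steps is invalid.** Section 9.3 asks for placebo against sirolimus. No section sets a separate Phase 3 step baseline, and a single pre-study baseline is the more natural reading. Under it the baseline cancels (step 3). This objection stands for the treatment contrast. It does not rescue the per-person change in Table 3, where the baseline stays in. Nor does 9.3 specify the analysis that would make the baseline irrelevant.

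**That the objective on walking fails.** Section 4.0 states "Aim 3: To assess improvement in walking ability" without naming an outcome for it. Table 3 puts the Fitbit under lesional severity. FHSQ foot function and the dynamic plantar-pressure scan also bear on walking. Steps are the only outcome that counts actual walking, so the link is reasonable, but it is an inference.

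**Conclusion.** The concern holds in a limited form. The outcome is defined against a baseline that the plan neither specifies nor secures: 0 to 42 untreated days before Phase 1, with none guaranteed, against 28 to 42 before Phase 3. The per-person change from baseline cannot be relied on as written. An analysis with period-specific baselines would treat the two periods unequally, with attenuation of 0 to 25% if up to half the effect were already present in the substitute baseline. That fraction is an assumption, as are the CV and the independence of days behind the standard errors. The direct within-person comparison of end-of-treatment steps is unaffected.

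This is a secondary outcome in a pilot of 8–10 participants, so the point is moderate. It is still more than missing detail: following the schedule to the letter yields no valid baseline. The plan should be changed before the first participant is dosed.

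**What to change.** **Preferred.** In Section 8.4 (item 5) and Table 3 (item e), define the treatment comparison as mean daily steps over the last 14 days of each treatment period, compared within participant. Anchor the window to that participant's actual end of treatment. Calendar weeks will not do: with a 6-week wash-out, Phase 3 ends at Week 12 + 6 + 12 = 30, and a window fixed at Weeks 26–28 would miss the last 14 treated days. The cost is wording only, because steps are already recorded daily.

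**If change from baseline is kept.** Issue the Fitbit after consent and at least 7 days before the first dose, inside the screening window that 6.1 already allows. Use those days as the baseline, and the last 7 wash-out days if a Phase 3 baseline is used. State the minimum number of valid wear days. Reconcile Table 2 with 6.1 and 6.4, so that consent and device issue are shown before the first application. The cost is consent and device delivery about a week earlier.

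The 7- and 14-day windows are a judgement and could reasonably differ. The essential step is to fix them in advance and apply the same rule in both periods.

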8.5 Safety Assessments

Safety and tolerability of the medication will be assessed at each visit through recording of adverse events, serious adverse events, evaluation of systemic absorption through measurement of trough sirolimus levels in serum, and additional safety laboratory tests listed below will also be performed.

Investigator assessment of local skin reaction (including increased erythema, edema, weeping/exudates, flaking/scaling/dryness, scabbing/crusting, and erosion/ulceration) will be assessed independently of other adverse effects.

Serum sirolimus levels

Trough serum sirolimus levels are a frequently run outpatient laboratory ELISA assay and will be performed at Stanford University at specific study visits from baseline.

Other Safety Laboratory Assessments

The clinical safety laboratory parameters will be assessed at each study visit. Laboratory tests may be repeated more often if clinically indicated.

All out-of-normal range laboratory values must be evaluated by the Investigator or subinvestigator as to whether they are clinically significant (i.e., require medical intervention or have clinical signs and/or symptoms). Abnormal clinical laboratory parameters that are considered clinically significant by the Investigator will be recorded on the Adverse Event (AE) Case Report Form (CRF) except Baseline visit. Clinically significant laboratory abnormalities noted from the Baseline visit will be recorded as medical history. The AE should be reported as a clinical diagnosis when possible. Laboratory tests will be performed at Stanford Children's Health clinics.

Urine Pregnancy Tests (UPT) will be performed at each scheduled visit on female subjects of childbearing potential starting at Baseline. If a UPT results in a positive test, the subject must be discontinued.

Sample management (collection, storage, shipping, etc...) will be done according to Stanford Clinical Laboratories standards and policies.

Clinical safety laboratories will include:

- Full blood count (CBC, Metabolic Panel, Liver function tests)
- Lipid panel profile
- Urinalysis
- Sirolimus trough (at specific study visits)

These will be performed at each scheduled study visit from screening/baseline visit (7 total), except for sirolimus trough.

Adverse Events (AE) and Serious Adverse Events (SAEs)

1. AE frequency, severity, and relationship to IMP.
2. Frequency of withdrawals due to treatment-related AEs.
3. Frequency of serious adverse events (SAEs)

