5.4 Withdrawal from the study

Participants must discontinue investigational medicinal product (IMP) and be withdrawn from the study for the following reasons:

- Participant withdraws consent
- Investigator request e.g. non-compliance with visits
- Participant meets any of the above exclusion criteria

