8.7 Adverse Events (AE) and Serious Adverse Events (SAEs)

The investigator is responsible for detecting, documenting, and reporting events that meet the definition of an AE or SAE. AEs will be collected from the start of study treatment through the protocol-specified follow-up period.

Definition of an AE: Any untoward medical occurrence in a subject or clinical investigation subject, temporally associated with the use of a medicinal product, whether or not considered related to the medicinal product.

Note: An AE can therefore be any unfavorable and unintended sign (including an abnormal laboratory finding), symptom, or disease (new or exacerbated)

temporally associated with the use of a medicinal product. This also includes failure to produce expected benefits (i.e. lack of efficacy), abuse, or misuse.

A serious adverse event (SAE) is any untoward medical occurrence that:

- a. Results in death
- b. Is life-threatening
- c. Requires hospitalization or prolongation of existing hospitalization
- d. Results in disability/incapacity, or
- e. Results in a congenital anomaly/birth defect

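### Section 8.5 counts withdrawals only for adverse events judged treatment-related, so this supporting tolerability measure can understate AE-driven withdrawals

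*Combined protocol and SAP*

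**What the plan says.** Under its adverse event heading, section 8.5 (Safety Assessments) lists three measures:

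- item 1: "AE frequency, severity, and relationship to IMP";
- item 2: "Frequency of withdrawals due to treatment-related AEs";
- item 3: the frequency of serious adverse events.

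Section 8.7 defines an AE as an untoward occurrence "temporally associated with the use of a medicinal product, whether or not considered related to the medicinal product". It also counts failure to produce the expected benefit as an AE.

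Section 5.4 gives three grounds for stopping study treatment and being withdrawn: "Participant withdraws consent", "Investigator request e.g. non-compliance with visits" and "Participant meets any of the above exclusion criteria". Section 7.4 adds that if the blind is broken during treatment, "the participant in question will be withdrawn from the treatment period and moved into the follow-up period". It makes emergency unblinding available so that an emergent adverse experience can be treated.

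Section 8.3 names as its second primary outcome "Safety and tolerability of topical sirolimus 2% ointment (serum trough sirolimus levels, monitoring for adverse events". Neither that entry nor the matching row of Table 3 mentions withdrawals. The withdrawal count appears only in section 8.5.

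**The concern.** A withdrawal enters item 2 only if someone judges that the AE behind it was caused by treatment. The documents themselves show why that judgement is difficult here. Section 2.1 names infection among the causes of early mortality in EBS, while section 2.2 lists opportunistic infection and delayed wound healing among the effects of systemic sirolimus. Section 8.6 grades EBDASI feet activity on blisters and erosions, while section 8.5 lists erosion and ulceration among the local skin reactions to be assessed. The same finding on the sole can be read as disease or as a treatment effect. The plan gives no criteria for deciding, and section 7.4 keeps the investigator blinded.

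A participant who stops because of a foot infection put down to EBS would therefore not appear in the only withdrawal measure the plan lists. Safety is Aim 1 (section 4.0), and stopping because of an AE is a direct sign of poor tolerability. In a trial of 8 to 10 people, one such case visibly changes the reported rate.

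**Working it through.** The plan gives no expected or tolerated withdrawal rate, so there is no figure of its own to reproduce. The sample size in section 9.2 concerns foot function and is not an input here.

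**Step 1: what each listed measure covers.**

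| Section 8.5 item | Causality filter | Counts withdrawals |
|---|---|---|
| 1. All AEs, with severity and relationship | No | No |
| 2. Withdrawals | Yes, treatment-related only | Yes |
| 3. Serious AEs | No | No |

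No row combines no filter with withdrawals. The withdrawals in item 2 are a subset of all AE-driven withdrawals, so the item 2 count is at most the full count.

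**Step 2: size of one uncounted case.** The planned sample is 8 to 10 (section 5.1). One participant is 1/8 = 12.5 percentage points, or 1/10 = 10 percentage points.

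**Step 3: an illustration with assumed events.** Suppose 2 of 8 participants stop for foot infection and both infections are judged unrelated. Exact (Clopper-Pearson) 95% intervals:

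- item 2 as written: 0/8 = 0%; upper limit 1 − 0.025^(1/8) = 36.9%;
- withdrawals for any AE: 2/8 = 25%; interval 3.2% to 65.1%.

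These are two different quantities and the intervals overlap widely. The example shows how the reported figure could differ, not that it will.

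**Step 4: chance of missing at least one case, over an assumed range.** Let p be the probability that a participant withdraws for an AE and u the share of those withdrawals judged unrelated. Neither is in the documents; take p from 0.10 to 0.30 and u from 0.25 to 0.50. With N participants, P(at least one missed) = 1 − (1 − pu)^N.

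| N | p = 0.10, u = 0.25 (pu = 0.025) | p = 0.20, u = 0.50 (pu = 0.10) | p = 0.30, u = 0.50 (pu = 0.15) |
|---|---|---|---|
| 8 | 18% | 57% | 73% |
| 10 | 22% | 65% | 80% |

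**Step 5: can the vehicle comparison replace causality judgement?** Suppose two participants withdraw for an AE on sirolimus and none on placebo. The exact paired (McNemar) two-sided p-value is 2 × 0.5² = 0.50. In addition, a participant who leaves in Phase 1 never receives the second treatment, so has no within-person comparison. An unfiltered count by treatment is informative, but at this size it cannot settle attribution.

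**The case against.** The strongest reply is that little is lost. Item 1 records all AEs with their relationship, item 3 counts serious AEs without a filter, local skin reactions are assessed separately from other adverse effects, and erythema is measured by Mexameter at each in-person visit. An infection or erosion judged EBS-related still enters these data. With 8 to 10 participants, each withdrawal can also be listed individually. All of this stands, and it is why the point is minor. It does not fill the gap, because none of those measures is tied to withdrawal.

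Four stronger readings are tempting, and the documents do not support them.

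- *The count belongs to a co-primary outcome.* The plan does not use that term, and neither section 8.3 nor Table 3 names withdrawals. Item 2 is a supporting measure in section 8.5.
- *Section 5.4 hides AE withdrawals.* It says when participants must stop; it is not a list of recording codes, and the CRF is not in the documents. Investigator request is open-ended, and the exclusion criteria in section 5.3 include allergy to the ointment and serious illness or infection posing a safety risk. Under section 7.4 an adverse experience is itself the stated ground for emergency unblinding. Item 2 could not be computed at all unless an AE could be linked to a withdrawal.
- *The unfiltered sirolimus-placebo comparison is discarded.* Only the withdrawal count is filtered; AEs and SAEs are not.
- *Comparison with vehicle makes causality assessment unnecessary.* Step 5 of the working shows that it cannot at this sample size. The blinded judgement remains useful and should be kept.

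**Conclusion.** The concern holds as a narrow, minor point. As written, item 2 can only equal or understate AE-driven withdrawals, and no other listed measure supplies the full count. This follows from the text alone. The size per case, 12.5 percentage points with 8 participants and 10 with 10, is arithmetic on the planned sample. The number of cases missed is not known: the 0/8 against 2/8 contrast and the 18% to 80% range rest on assumed event rates and an assumed share judged unrelated. A reader should not infer that the reported rate will be driven to zero; the documents give no figure for how often such events would be judged unrelated. No efficacy analysis and no AE record is affected.

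**What to change.** Reword section 8.5 item 2 along these lines: *number of participants who stop IMP or leave the study with any AE as a reason or contributing reason, whatever the judged relationship, by the treatment in use (or last used) at AE onset; the subset judged treatment-related is shown beneath.* The present measure is kept as that subset.

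Let the withdrawal record accept adverse event as a contributing reason alongside the routes in sections 5.4 and 7.4, so that a participant who withdraws consent or is unblinded because of an AE can be identified. Because section 8.7 treats lack of efficacy as an AE, show the AE term for each case so that readers can tell those withdrawals apart.

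This changes what is recorded and counted, not who is stopped. The cost is one CRF field, one table definition and a reported rate that may look less favourable. No extra visits or data sources are needed.
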